7 STATISTICAL ANALYSES

SAS® version 9.2 or higher will be used for statistical analyses, tabulations, and graphical presentations.

7.1 General Methods

The data from the subjects who were enrolled at Site 2 will not be included in any summaries or statistical analyses. These data will only be presented in the listings. Details of the data presentation are specified in the DPP. The data from the 30 replacement subjects along with the data from the initial 116 subjects who were enrolled and dosed at the other sites will be used for analyses.

All data recorded on case report forms will be listed by subject. Descriptive summaries will be presented for continuous variables using number of subjects (N), mean, standard deviation (SD), median, minimum and maximum. Geometric mean and coefficient of variation (CV%) will also be presented for sample serum concentration-time data and PK parameters. Descriptive summaries for categorical variables will utilize counts and percentages.

For all treatment comparisons, a linear fixed effect model with treatment as a fixed effect will be fitted to the log-transformed PK parameters C_{max}, AUC(0-T) and AUC(INF) for use in estimation of effects and construction of CIs. Point estimates and 90% CIs for differences on the log-scale will be exponentiated to obtain estimates for ratios of geometric means and respective 90% confidence intervals on the original scale. The SAS procedure (PROC MIXED) will be used to derive all inter-subject variances, and for the estimation of test to reference ratios and respective confidence intervals.

Adverse events and medical history will be coded according to the most recent Medical Dictionary for Regulatory Activities (MedDRA) version. Previous and concomitant medications will be coded using the BMS Drug Dictionary.

7.2 Study Conduct

Relevant deviations from the study protocol, protocol amendments and administrative changes will be documented and accounted for in presenting the data summaries, listings and descriptive statistical analyses. Deviations of protocol-specified inclusion and exclusion criteria, and protocol deviations as recorded on a log maintained by the clinical monitors, will be listed. Any

changes from planned protocol-specified analysis, if any, will be defined in the SAP and reported in the clinical study report (CSR).

7.3 Study Population

7.3.1 Subject Disposition

Subject disposition will be listed. Summary tables reflecting the number of subjects who are enrolled, who are randomized, reasons for not being randomized, who are treated, and who completed the study will be presented as overall.

The number of subjects who do not complete the study, both overall and according to reasons for discontinuation from the study, will be summarized for all treated subjects, as overall and by treatment.

7.3.2 Demographic Characteristics

Demographic characteristics such as gender, age, race and ethnicity will be listed for all treated subjects. Demographic characteristics will also be summarized for all treated subjects, as overall and by treatment.

7.3.3 Physical Measurements

Physical measurements such as body weight, height and body mass index (BMI) will be listed for all treated subjects. Measurements will also be summarized by nominal visit for all treated subjects, as overall and by treatment.

7.3.4 Medical History and Previous Medications

Medical history and previous medications taken prior to dosing will be listed for all treated subjects.

7.4 Extent of Exposure

No analysis regarding extent of exposure is planned. Study drug administration, randomization schedule, and batch numbers will be documented as per subject listings. Any non-study medications taken by subjects, any conducted non-study medical treatment procedures, and any utilized non-study diagnostic procedures will also be listed.

7.5 Efficacy

There are no efficacy assessments in the study.

7.6 Safety

Analysis of all safety data will follow the BMS guideline of analysis of safety data⁷.

The evaluation of safety is based on clinical AEs, vital signs, ECG results, clinical laboratory results, and physical examination findings reported during the study. Unless otherwise specified, all safety presentations will utilize the treated population as described in [Section 6.3](#).

All recorded AEs will be listed and tabulated by system organ class (SOC), preferred term (PT), treatment and overall. Any physical examination findings will be listed. ECG, vital signs and clinical laboratory test results and corresponding change from baseline values will be listed and

summarized by treatment and visit. Values for ECG, vital signs and clinical laboratory test results outside the pre-specified criteria will also be listed and summarized. Electrocardiogram readings will be evaluated by the investigator and abnormalities, if present, will be listed.

Where appropriate, baseline is defined as the last non-missing result with a collection date-time less than the date-time of the first active dose of study medication, for laboratory results, vital signs, and ECG results.

7.6.1 Deaths

All reported deaths after a subject is enrolled (i.e., has signed the informed consent) will be listed separately by subject.

7.6.2 Serious Adverse Events

All reported SAEs will be listed and summarized for all enrolled subjects.

7.6.3 Adverse Events

All AEs will be coded and grouped into PT by SOC, using MedDRA. Listings and summaries will be based on the resulting SOCs and PTs.

Adverse events which occur on or after the first dose of study treatment will be tabulated. Events will be assigned to the study treatment administered to the subject. Events occurring after discharge will be assigned to the study treatment received for SAEs reported through Day 101 after the dose of the study drug and non-serious AEs that are reported through Day 71 after the dose of the study drug. The proportion of subjects having an AE will be calculated as the number of subjects experiencing the event, divided by the total number of subjects receiving study treatment.

All AE listings will indicate the unique subject identifier, age, gender, current treatment, the date of onset, the date of resolution, day of onset relative to the start of treatment, action taken, investigator's assessment of severity and relationship to study drug. Additional listings will be provided for AEs leading to discontinuation and AEs without recorded resolution. Summaries of AEs will include AEs, AEs by intensity and AEs by relationship.

Where a subject has the same AEs, based on preferred terminology, reported multiple times in a single analysis period, the subject will only be counted once at the preferred terminology level in AE frequency tables.

Where a subject has multiple AEs within the same SOC in a single analysis period, the subject will only be counted once at the SOC level in AE frequency tables.

When a subject has the same AE, based on preferred terminology, reported multiple times in a single analysis period, the following criteria, in order of precedence, will be used to select the event to be included in summary tables:

- Relationship to study medication
- Intensity of event
- Onset date and time

When reporting AEs by intensity, in addition to providing a summary table based on the event selection criteria detailed above, summary tables will also be provided based on the most intense event during the analysis period - independent of relationship to study medication. For these tables, the following criteria, in order of precedence, will be used to select the event to be included in summary tables:

- Intensity of event
- Onset date and time

Subjects will only be counted once in the ‘Total’ at their maximum intensity, regardless of SOC or PT.

7.6.4 Clinical Laboratory Evaluations

The results of all protocol-specified clinical laboratory tests, as well as laboratory results outside of the normal range, will be listed. Scheduled laboratory measurements and corresponding change from baseline values will be summarized by treatment and nominal visit for each laboratory test. Laboratory evaluations will be reported both in conventional units and in SI units.

Laboratory results will be classified as markedly abnormal based on sponsor-defined criteria. The criteria will be listed.

Laboratory results for subjects with any marked laboratory abnormality (scheduled and unscheduled) will be listed. This listing will include all observations for the specific laboratory test and subject, not only the marked laboratory abnormalities. The frequency of subjects with any marked laboratory abnormality as well as hematology, serum chemistry, and urinalysis marked abnormalities, based on pre-specified criteria, will be presented.

Laboratory results will be listed for subjects with ALT results greater than 3 times of upper limit of normal (ULN) and total bilirubin results greater than 2 times of ULN on the same date. This listing will include all observations for ALT, total bilirubin, AST, and alkaline phosphatase for the above mentioned subjects.

Pregnancy results will be listed.

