6.6 Potential Drug Induced Liver Injury

Wherever possible, timely confirmation of initial liver-related laboratory abnormalities should occur prior to the reporting of a potential DILI event. All occurrences of potential DILIs, meeting the defined criteria, must be reported as SAEs (See Section 6.1.1 for reporting details).

Potential DILI is defined as:

- 1) Aminotransaminases (ALT or AST) elevation > 3 times ULN
AND
- 2) Total bilirubin > 2 times ULN, without initial findings of cholestasis (elevated serum alkaline phosphatase),
AND
- 3) No other immediately apparent possible causes of aminotransaminase elevation and hyperbilirubinemia, including, but not limited to, viral hepatitis, pre-existing chronic or acute liver disease, or the administration of other drug(s) known to be hepatotoxic.

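### The SAP's joint liver listing selects on ALT alone, so a same-date AST-only case that meets the protocol's laboratory thresholds for potential DILI is not picked out

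*SAP*

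**What the plan says.** SAP 7.6.4 (Clinical Laboratory Evaluations) describes one output that combines an aminotransferase with bilirubin. It lists subjects with "ALT results greater than 3 times of upper limit of normal (ULN) and total bilirubin results greater than 2 times of ULN", and the bilirubin condition is tied to timing: "greater than 2 times of ULN on the same date". What is printed for them is broader than what selects them: "This listing will include all observations for ALT, total bilirubin, AST, and alkaline phosphatase for the above mentioned subjects". AST is thus a displayed analyte and not a selection criterion.

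Protocol 6.6 (Potential Drug Induced Liver Injury) has three conditions. The first is "Aminotransaminases (ALT or AST) elevation > 3 times ULN". The second is "Total bilirubin > 2 times ULN, without initial findings of cholestasis (elevated serum alkaline phosphatase", with the bracket closing there. The third is that no other cause is immediately apparent. Section 6.6 requires events meeting the definition to be reported as SAEs, and protocol 6.1 says the same of potential DILI in general.

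Three other planned outputs bear on the point:

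- SAP 7.6.4, general listing: "The results of all protocol-specified clinical laboratory tests, as well as laboratory results outside of the normal range, will be listed".
- SAP 7.6.4, marked abnormalities: "Laboratory results for subjects with any marked laboratory abnormality (scheduled and unscheduled) will be listed". The criteria are left outside the text: "Laboratory results will be classified as markedly abnormal based on sponsor-defined criteria".
- SAP 7.6.2: SAEs that are reported will be listed and summarized for the enrolled subjects.

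**The concern.** The two documents use the same numerical cut-offs for the same pair of laboratory signals, but the SAP's rule is narrower in its aminotransferase term. The protocol treats an AST elevation as sufficient; the SAP's listing does not. The SAP gives no reason for leaving AST out of the selection while printing it for selected subjects.

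At stake is how easily a case is found. The general and out-of-range listings show individual values and leave the reader to notice that two of them coincide. The marked-abnormality listing is described test by test. The SAE listing holds only what sites have reported. In the SAP as it can be read, the 7.6.4 joint listing is the only output that applies the combined criterion by program, and it would pass over an AST-only case.

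**Working it through.** No sample size, power or error rate is involved, and the plan gives no figure to reproduce. The check is a comparison of two selection rules.

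**Inputs**

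- SAP 7.6.4 rule: ALT > 3 × ULN, and total bilirubin (TB) > 2 × ULN, and same date.
- Protocol 6.6, laboratory part: (ALT > 3 × ULN or AST > 3 × ULN), and TB > 2 × ULN. The cholestasis and other-cause conditions are taken as met. Section 6.6 states no timing.
- Data available: protocol 5.3.2 puts ALT, AST, total bilirubin and alkaline phosphatase on the same serum chemistry panel.

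**Step 1: same-date results.** The multiples of ULN below are illustrative values on either side of each threshold.

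| ALT | AST | TB | SAP 7.6.4 selects | Protocol 6.6 thresholds met |
|---|---|---|---|---|
| 2.5 | 2.5 | 1.5 | no | no |
| 2.5 | 2.5 | 2.5 | no | no |
| 2.5 | 3.5 | 1.5 | no | no |
| **2.5** | **3.5** | **2.5** | **no** | **yes** |
| 3.5 | 2.5 | 1.5 | no | no |
| 3.5 | 2.5 | 2.5 | yes | yes |
| 3.5 | 3.5 | 1.5 | no | no |
| 3.5 | 3.5 | 2.5 | yes | yes |

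The rules differ in one of the eight rows, the AST-only row.

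**Step 2: AST added to the SAP rule.** With (ALT or AST) > 3 × ULN, and TB > 2 × ULN, and same date, the AST-only row becomes yes. No other row changes, and the two rules agree in all eight.

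**Step 3: results on different dates.** The SAP rule then selects nobody. If 6.6 is read as having no timing condition, the rules also differ wherever bilirubin and at least one aminotransferase are above threshold on separate dates. That difference comes from the same-date condition, not from the ALT/AST wording. Since 6.6 says nothing about timing, it is not a contradiction.

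**Step 4: where an AST-only case would still appear.** AST above 3 × ULN and bilirubin above 2 × ULN are each outside the normal range, so both are in the general and out-of-range listings. They are in the marked-abnormality listing if they meet the sponsor's criteria, which the SAP does not give. If the site reports the event as potential DILI, it is in the SAE listing and summary.

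**Step 5: how often.** The documents give no incidence, so no expected count can be computed. Protocol 3.3.2 excludes subjects whose ALT, AST or total bilirubin is above ULN on a confirmed pre-dose test, and the study gives one dose to healthy volunteers.

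**The case against.** The strongest reply is that the two rules serve different purposes. Protocol 6.6 defines an event that the investigator must report; SAP 7.6.4 describes a listing for the study report. The SAP does not call it a DILI listing or refer to 6.6. The listing also leaves out the cholestasis and other-cause conditions and adds a same-date condition that 6.6 lacks. ALT-only selection may be deliberate. Subject safety rests on SAE reporting, not on a listing produced after database lock. SAP 7.6 also defers to a sponsor guideline on safety analysis, and SAP 8 defers output details to a Data Presentation Plan. Neither is available here, so an AST trigger in either can be neither confirmed nor ruled out.

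Most of this stands, and it limits the point in three ways. A reader might infer that the SAP contradicts the protocol's DILI definition; the documents do not support that, because the listing never claims to apply the definition. A reader might infer that AST-only cases would be lost or go unreported; they would not, given the other listings and the SAE requirement. A reader might also count the same-date condition as a second error; with no timing in 6.6, it is not one.

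What the reply does not remove is the stated selection rule itself. This is not a detail left for later: the SAP names the trigger, and the trigger omits an analyte that the protocol treats as sufficient, although that analyte is measured on the same panel and already printed in the same listing.

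**Conclusion.** The point holds as a small mismatch in one listing. A subject with AST above 3 times ULN, ALT at or below that level and total bilirubin above 2 times ULN on one date meets the protocol's laboratory thresholds for potential DILI and is not selected by SAP 7.6.4. Among same-date results this is the only pattern on which the two rules part.

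The practical effect is limited to a case that occurs, is AST-only, and is not reported by the site. Its frequency cannot be computed and is likely very low. The primary PK analysis and the biocomparability conclusion are untouched.

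The conclusion rests on the readable text of SAP 7.6.4 and protocol 6.6, with the two non-laboratory conditions of 6.6 taken as met. If the Data Presentation Plan or the safety guideline already selects on AST, the change below only brings the SAP's wording into line. It is worth considering because it is cheap, not because the risk is large.

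**What to change.** In SAP 7.6.4, change the selection to: ALT or AST greater than 3 times ULN, and total bilirubin greater than 2 times ULN, on the same date.

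Leave the rest of the listing as it stands: the same-date rule, the period covered, and the display of all ALT, AST, total bilirubin and alkaline phosphatase results for selected subjects. The cholestasis and alternative-cause conditions of protocol 6.6 stay with medical review and need not be programmed.

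The cost is one line of SAP text and a small edit to the listing program. The downside is possibly a few extra subjects to review; the documents do not allow that number to be computed.

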7.6.5 Electrocardiograms

All recorded ECGs will be listed. The investigator identified ECG abnormalities will be listed.

If QT interval corrected for heart rate using the Fridericia formula (QTcF) is not available in the database, QTcF will be calculated using the reported uncorrected QT interval and heart rate, and the following formula:

$$QTcF = \frac{QT}{(60/HEART\ RATE)^{1/3}}$$

If QT corrected for heart rate using the Bazett formula (QTcB) is not available in the database, QTcB will not be calculated.

Summaries of ECG parameters (heart rate (HR), QT (QT, QTcF), PR and QRS intervals) will be tabulated by study day and treatment. Summaries of ECG parameters will include change from baseline at end of study.

Subjects with ECG intervals outside of a pre-specified range will also be listed.

The following criteria will be used to determine ECG results that are outside of a pre-specified range:

[REDACTED]	[REDACTED]

7.6.6 Vital Signs

Vital signs parameters (systolic blood pressure (BP), diastolic BP, heart rate, respiratory rate, and body temperature) will be listed. Summaries of vital sign parameters will be provided for each vital sign parameter at corresponding visits by treatment and respective changes from baseline.

Subjects with vital signs outside of a pre-specified range will also be listed.

The following criteria will be used to determine vital sign results that are outside of a pre-specified range, where changes from baseline are based on matched postural positions and are calculated as parameter value - baseline parameter value:

[REDACTED]	[REDACTED]

7.6.7 Physical Examination Findings

All physical examination abnormal findings will be listed per subject and visit.

7.7 Pharmacokinetics

The PK population will be used for all listings. Evaluable PK population will be used for summary statistics and statistical analyses. Analysis will include all analyte data in the PK dataset for belatacept.

Subject serum concentration-time data will be listed and summarized by treatment and nominal collection time for belatacept. Details of T-HALF derivation and the harmonic mean of terminal slope by treatment will also be presented. Plots of individual serum concentration profiles over time will be provided. Overlay of individual serum concentration profiles over time will be provided by treatment. Plots of mean (+SD) serum concentration profiles versus time will be presented for belatacept, and both treatments will be superimposed on the same plot.

All individual PK parameters will be listed for belatacept including any exclusions and reasons for exclusion from summaries. Summary statistics will be tabulated for each PK parameter by treatment. Geometric means and CV% will be presented for Cmax, AUC(0-T), AUC(INF), CLT, and Vss. Medians and ranges will be presented for Tmax. Arithmetic mean and standard deviation will be presented for T-HALF. Decimal place specifications for summary statistics are described in Section 7.10.

Separately by antibody status (negative antibody status with respect to baseline as defined in Section 7.9) and overall, a linear fixed effect model with treatment as a fixed effect will be employed. Kenward-Rogers degrees of freedom will be specified in the model. Point estimates and 90% CIs for treatment differences on the log-scale will be exponentiated to obtain point estimates and 90% CIs for the ratios of geometric means on the original scale. A sensitivity analysis comparing the PK between Process E and Process C may be performed by excluding patients who are positive for anti-belatacept antibodies. The following SAS code will be implemented, where A is the Process E belatacept, and B is the Process C belatacept.

Plots of individual Cmax, AUC(0-T) and AUC(INF) combined with corresponding geometric means will be provided versus treatment.

In addition, the impact of anti-belatacept antibody status on PK parameters will also be evaluated in individual subjects. Summary statistics may be tabulated for each PK parameter by antibody status for each treatment. Plots of individual PK parameters versus treatment by antibody status may be provided. Refer to Section 7.9 for the definition of positive antibody status for each subject.

7.8 Biomarkers

No biomarker assessments are scheduled for this study.

7.9 Immunogenicity

7.10 Conventions

Enhanced Biometric Analysis & Reporting Capability (EmBARC) standard time windowing, imputation rules, and counting rules will be applied.

7.10.1 Decimal Places

The number of decimal places displayed in efficacy, safety, and biomarker listings will be determined by the number of decimal places in the raw data.

Unless otherwise specified, minimum and maximum will be reported to the precision as the data collected, one more decimal place for the mean and median, and two more decimal places for the standard deviation. The adjusted geometric mean, geometric mean ratio and the lower and upper limits of CI will be displayed to three decimal places.

7.10.2 Pharmacokinetic Summaries

In-text Tables

For in-text PK tables, CV% will be reported as integers. For other statistics except for standard deviations, values of 100 or higher will be presented as integers, values of 10 - <100 will be displayed to one decimal place, and values of 1 - < 10 will be displayed to two decimal places.

Values less than 1 will be displayed to three decimal places. Ratios will also be displayed to three decimal places. Standard deviations will be reported to a precision of 1 decimal place more than the mean.

Handling of Non-Quantifiable Concentrations⁸

For the summaries of serum concentration-time data, concentrations that are less than the lower limit of quantification (LLOQ) should be displayed as “< LLOQ” in the listings and be treated as missing in summary tables and plots. For the purpose of calculating PK parameters, pre-dose concentrations that are less than LLOQ and concentrations prior to the first quantifiable concentration that are less than LLOQ will be set to zero, and all other concentrations less than LLOQ will be set to missing.

All available serum concentration-time data and derived PK parameter values will be included in the PK data set and listed accordingly.

Treatment of Outliers

Individual serum concentrations, if deemed to be anomalous, may be excluded from the analysis following a review of available documentation (e.g., bioanalytical report, clinical data). Any such exclusion will be clearly listed in the study report along with justification for exclusion.

Entire serum concentration-time profiles for a subject may be excluded following review of available documentation (e.g., bioanalytical report, clinical data). However, results of analysis with and without the excluded profiles may be presented in the study report. Any such exclusion will be clearly listed in the study report along with justification for exclusion.

PK Exclusions⁸

PK Analysis, Reporting, and Exclusion criteria should follow the BMS PK Harmonization document Version 3.0. Specific guideline for exclusionary criteria for half-life and how other PK parameters are affected for exclusion is under section 6.2 of the BMS PK Harmonization document.

